1.4 Potential Risks

1.4.1 Complications of Spinal Cord Injury

There are many medical complications that affect individuals who have suffered a traumatic spinal cord injury. These risks include, but are not limited to:

- allodynia
- anemia
- autonomic dysreflexia
- bowel dysfunction
- deep vein thrombosis (DVT) with or without pulmonary embolism

- hemorrhoids
- heterotopic ossification
- hyperthermia
- hypotension
- hypothermia
- pain
- pressure ulcers
- respiratory depression/dysfunction
- respiratory infections
- spasticity
- syringomyelia
- tachycardia
- urinary tract infections

Development of any one or more of the complications noted above will be considered an anticipated (expected) adverse event (AE) in this study. Risks that are specific to AST-OPC1 are described below, and they fall into three categories: 1) risks related to the surgical procedure for AST-OPC1 injection, 2) risks secondary to immunosuppression, and 3) potential risks of the AST-OPC1 cells.

1.4.2 Surgical Injection Procedures

AST-OPC1 is injected directly into the spinal cord during an open surgical procedure under general anesthesia. The procedure requires a posterior approach, laminectomy, and opening of the dura. These steps are common in intradural spinal cord operations, and have several known risks, including:

- anesthesia-associated risks
- compression of nerve roots
- CSF leak
- deep vein thrombosis and pulmonary embolus
- further tissue damage to the spinal cord
- hemorrhage and/or fluid collection in tissues between the incision site and the spinal cord
- infection (incision site, intraspinal/CNS, pneumonia, urinary tract)

- intraspinal hemorrhage
- pain
- spinal cord tethering

These risks will be minimized as much as possible by selecting participating sites with highly qualified spine surgeons and ensuring good perioperative care. In the previous thoracic study of AST-OPC1 (Geron Protocol CP35A007), there were no serious or unexpected adverse events related to the injection procedure. There were 9 AEs in that study that were judged to be possibly related to the injection procedure. These were all Grade 1 or Grade 2 in severity and were predominantly transient postoperative pain, one brief, mild, elevated temperature, and one urinary tract infection.

1.4.3 AST-OPC1

As outlined in Section 1.2.6, clinical experience has been obtained in 5 subjects with thoracic SCI in Geron Protocol CP35A007. There were no serious or unexpected adverse events related to AST-OPC1, nor was there any evidence of cyst formation or enlarging masses at the injection sites on MRI scans. At this stage, all potential risks discussed below are theoretical.

Based on the results of nonclinical studies, the potential risks of AST-OPC1 include the formation of ectopic tissue (atypical glandular structures and/or cartilaginous tissue) at the injection site and/or teratomas. Since no teratomas were observed in any animals injected with AST-OPC1 from lots that are intended for clinical use, the estimated likelihood of this risk in human subjects is very low. In addition, the foci of ectopic tissue that were observed were all contained within AST-OPC1 grafts and were much smaller (< 1 mm diameter) than the lesion cavities in control animals.

If an area of ectopic tissue develops, it is possible that this ectopic tissue may not reach a size that is detectable on magnetic resonance imaging (MRI) (about 1–2 mm in length) until after 1 year following AST-OPC1 injection. In contrast, many individuals with SCI have lesion cavities in the spinal cord that are at least several millimeters in length and/or damaged spinal tissue that may exhibit areas of heterogeneous signal on MRI. In addition, approximately 21–28% of all individuals with SCI will develop progressive posttraumatic cystic myelopathy (PPCM), also known as posttraumatic syringomyelia (Brodbelt 2003) in which the initial lesion cavity expands and causes further destruction of spinal tissue above and/or below the original injury level. Development of PPCM is usually slow, with a median time of onset at 20 months after injury (Edgar 1994). Only about 1–9% of individuals with **Amendment 3: 07 July 2017 Confidential Page 30 of 84**

SCI will develop clinical symptoms due to PPCM (Brodbelt 2003). These symptoms might include asymmetrical motor loss, increased pain or temperature sensitivity above the level of the lesion, increased spasticity, and autonomic dysreflexia.

In over 95% of PPCM cases, the cystic cavity attains a length of at least 4 cm before clinical symptoms become evident (Edgar 1994). No treatments are recommended for patients who have evidence of PPCM on MRI scans but do not have clinical symptoms.

1.4.3.1 Xenotransplantation Related Risks

Another theoretical risk of AST-OPC1 is that it may contain heretofore unknown and currently undetectable murine viral or retroviral adventitious agents. This theoretical risk is a consequence of the original culturing of the H1 uhESC line on a layer of irradiated murine (mouse) embryonic feeder cells. However, the H1 line was adapted to feeder-free culture conditions prior to generating the H1 Master Cell Bank (MCB) from which AST-OPC1 is produced. This MCB has been demonstrated to be free from known murine viral and retroviral adventitious agents. Precautions with regard to xenotransplantation that will be taken in this study are described in Appendix A.

Additional warnings and precautions are outlined in the Investigator's Brochure.

1.4.3.2 Reproductive Risks

Nonclinical studies of AST-OPC1 biodistribution following injection into the spinal cord have not shown evidence of quantifiable AST-OPC1 cells outside of the CNS. Thus, the potential reproductive risks of AST-OPC1 are unknown, but would theoretically decrease as the cells mature into adult oligodendrocytes, which are not found outside the CNS. In addition, very few proliferative cells are present in the AST-OPC1 grafts beyond six months post-injection.

The effects of AST-OPC1 on a fetus or nursing child are unknown. Pregnant or nursing women are excluded from this study because participation requires immunosuppression with tacrolimus and multiple MRI scans with gadolinium-DTPA contrast, both of which present potential additional risk to a pregnant subject.

1.4.4 Tacrolimus

Common adverse reactions to tacrolimus may be found in the package insert for tacrolimus and can include infection, malignancy, nephrotoxicity, hypertension, diabetes, neurotoxicity, and potassium imbalance (http://www.astellas.us/docs/prograf.pdf). Tacrolimus will be given for a finite duration (up through Day 60) and dose will be tapered after Day 46. Blood levels

of drug will be monitored throughout and doses adjusted accordingly to maintain levels between 3 and 7 ng/mL. Concomitant medications and food products will be monitored to avoid untoward interactions.

The tacrolimus regimen in this study is identical to that used in the previous thoracic SCI trial of AST-OPC1 (Geron Protocol CP35A007). There were no serious or unexpected adverse events related to tacrolimus in that study and all five subjects completed the course of tacrolimus per protocol. There were 16 adverse events reported as possibly related to immunosuppression with tacrolimus. These were all Grade 1 or Grade 2 in severity and were consistent with the common adverse reactions to tacrolimus including: nausea, urinary tract infection, and decreased magnesium blood level.

2 STUDY OBJECTIVES

The primary objective of this study is to evaluate the safety of 3 sequential escalating doses of AST-OPC1 administered at a single time-point between 21 and 42 days post-injury, inclusive, to subjects with severe, subacute cervical spinal cord injuries (SCI).

The secondary objective is to evaluate changes in neurologic function following administration of AST-OPC1.

3 INVESTIGATIONAL PLAN

3.1 Overall Study Design

This clinical development program includes 2 proof-of-concept companion trials that are designed to explore the safety and potential efficacy of AST-OPC1 in subjects with recent cervical spinal cord injuries, i.e., occurring between 21 and 42 days prior to AST-OPC1 administration. Study AST-OPC1-01 is a Phase 1/2a dose-escalation protocol encompassing injection (2×10^6 , 1×10^7 , or 2×10^7 AST-OPC1 cells) and 1 year of follow-up as described herein (See **Figure 3-1**). Study AST-OPC1-02 is a long-term follow-up protocol presented separately.

AST-OPC1-01 is an open-label, dose escalation, cross-sequential, multicenter Phase 1/2a study. Subjects with cervical AIS-A SCI will receive 1 of 3 sequential dose levels of AST-OPC1 injected directly into the spinal lesion within 21 and 42 days after the original injury. Subjects with cervical AIS-B SCI will receive 1×10^7 , or 2×10^7 AST-OPC1 cells. All subjects will also receive tacrolimus for 60 days following injection to prevent immune rejection. Subjects will be followed for safety and neurologic function for 1 year under this protocol and will then be required to participate in a separate long-term safety follow-up protocol for 14 years. In addition, eligible subjects who were enrolled and had DVT prophylaxis withdrawn prior to Day 1 but who never received the AST-OPC1 injection will be followed for safety for 30 days and assessed separately. All adverse events will be monitored in an ongoing fashion by the Sponsor's medical monitor and by an independent Data Monitoring Committee (see Section 7.14.1).

3.1.1 Staggered Enrollment within each Cohort

Enrollment in Cohort 1 will be staggered such that there are at least 10 days between administration of AST-OPC1 to each subject. Enrollment within Cohorts 2-5 will be staggered after the initial subject in each cohort is dosed, with at least 8 days between administration of AST-OPC1 to the first and second subjects. If the first two subjects are successfully dosed with no serious adverse events (SAEs) that would trigger study suspension (per the study Suspension Rules), then the remaining subjects in that cohort may be dosed without further staggering.

An additional staggering rule for Cohorts 2-5 is that a minimum of 14 days must elapse between the dosing of any two consecutive subjects who both have a C4 neurological level of injury (NLI). This 14-day stagger for consecutive C4 NLI subjects applies throughout each of these cohorts and also would supersede the 8-day stagger noted above if the first two subjects in any cohort both have a C4 NLI.

Figure 3-1: Study Schematic:

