3.1.2 Rules for Advancement to Cohorts 2-5

Enrollment in Cohort 2 may commence after all three subjects in Cohort 1 have completed 30 days of follow up after AST-OPC1 administration AND the safety data for Cohort 1 have been reviewed by the Data Monitoring Committee (DMC).

Enrollment in Cohort 3 may commence after at least five subjects in Cohort 2 have completed 30 days of follow up after AST-OPC1 administration AND the safety data from Cohorts 1 and 2 have been reviewed by the DMC.

Enrollment in Cohort 4 may commence after at least two subjects in Cohort 2 have completed 30 days of follow up after AST-OPC1 administration AND if there are no SAEs that would trigger study suspension.

Enrollment in Cohort 5 may commence after at least two subjects in Cohort 3 AND at least five subjects in Cohort 4 have completed 30 days of follow up after AST-OPC1 administration AND if there are no SAEs that would trigger study suspension.

For the planned DMC reviews noted above, the DMC will recommend whether enrollment of the next dose cohort can commence or whether additional follow up of the current cohort is needed prior to commencing enrollment in the next cohort. The rationale for the 8-day stagger (or the 14-day stagger between consecutive subjects with a C4 NLI) is that nearly all of the potential surgical complications, if they occur, will become clinically evident within the first few days after surgery. Thus, any serious complications (i.e., SAEs) would be evident within the first few days after surgery and would be reported within 24 hours of their occurrence (as required for all SAEs).

In addition, subjects in this study will receive a complete neurological exam and MRI scan for safety monitoring at 7 days after AST-OPC1 injection. The study suspension rules (See Section 7.14.2) include several rules that could be triggered by potential complications of the AST-OPC1 injection procedure, such as: death or unexpected neurological deterioration, evidence of direct spinal cord damage related to the volume of injection, or any CSF infection or inflammation that is more than a transient reaction to AST-OPC1 injection.

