5 ENROLLMENT

Site personnel should notify the Sponsor when screening initiates for an individual subject in order to ensure that the protocol specified rules for staggering within cohorts and for advancement to Cohorts 2-5 are followed correctly. This notification will also enable the Sponsor to ensure that the maximum number of subjects per each cohort is not exceeded.

After signing informed consent, potential subjects will be assigned a subject identification containing the site number and a sequential enrollment number. After eligibility assessment, subjects who are deemed eligible in accordance with the inclusion/exclusion criteria (Section 4) will be enrolled into the study.

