7.4 Post-Injection Days 1-6

- Brief physical exam on Day 1
- Vital signs daily
- Hematology (as before) on Day 1
- Restart DVT prophylaxis on Day 1 (if applicable)
- Blood chemistry (as before) daily
- Tacrolimus blood level on Day 3 (+/- 1 day)
- Concomitant medications
- Adverse events

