7.5 Post-Injection Day 7 (+/- 1 day)

- Brief physical exam and vital signs
- Neurological exam
- ISNCSCI exam
- MRI (cervical spine, with and without gadolinium-DTPA contrast)
- ECG
- Hematology (as before)
- Blood chemistry (as before)
- Tacrolimus blood level
- Blood for immune response monitoring
- Concomitant medications
- Adverse events

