7.14.2 Suspension Rules

The DMC will receive rapid notification of all SAEs associated with the use of AST-OPC1 and of all reports of cyst/cavity formation. The DMC will operate under a high degree of flexibility and will tend to err on the side of protecting subjects' safety until satisfactory resolution of potential problems is obtained. Any event that triggers study suspension will be reported to the FDA and to the IRBs. If study suspension occurs, both enrollment of new subjects and administration of AST-OPC1 will be suspended.

The following events will be used as study suspension rules:

• Death or unexpected neurological deterioration, possibly related to AST-OPC1, the injection procedure used to administer AST-OPC1, and/or the concomitant immunosuppression administered

- Evidence of direct spinal cord damage related to the volume of injection
- Development of an enlarging mass or expanding ectopic tissue within the central nervous system, other than the expected filling of the lesion cavity by AST-OPC1
- Any CSF infection or inflammation that is more than a transient reaction to AST-OPC1 injection.

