All MRI exams will include postcontrast (gadolinium-DTPA) T1-weighted images in the sagittal and axial planes with the same parameters used for the respective pre-contrast images (unless the subject is allergic to contrast).

Suggested MRI scans of the brain include routine T1-weighted and T2-weighted scans in the sagittal and axial planes, plus postcontrast T1-weighted images.

Central Reading of MRI Scans

All study-driven MRI reading will be performed by a central group of neuroradiologists with extensive experience in MRI evaluation of spinal cord trauma. The images will be sent to the central group electronically via an imaging contract research organization.

The poststabilization screening/baseline MRI scan will be used to determine the whether the following eligibility criteria are met:

- single spinal cord lesion on a post-stabilization magnetic resonance imaging (MRI) scan, with sufficient visualization of the spinal cord injury epicenter and lesion margins to enable post-injection safety monitoring
- absence of anatomical transection or significant laceration
- spinal cord lesion with anteroposterior diameter of the spinal cord ≥ 2 mm at point of maximal compression on a midline sagittal image from a poststabilization MRI

The screening/baseline MRI will also be used to make a preliminary determination of the target site for AST-OPC1 injection. This site should be near the caudal margin of the injury epicenter, and within damaged, but nonhemorrhagic tissue.

Several additional parameters may be measured for future research analyses. These may include:

- Length of contusion (ie, maximal extent of petechial hemorrhages)
- Presence/absence of intramedullary hemorrhage
- Length of intramedullary hemorrhage

- Length of edema
- Percent compression at epicenter

Following AST-OPC1 injection, the MR images will be assessed according to standard practice and with specific attention to the following potential risks:

- intramedullary hemorrhage, CSF leak, epidural abscess, infection
- evidence of expanding cyst or mass at the injection site or elsewhere in CNS
- evidence of inflammatory lesion(s) at injection site or elsewhere in CNS
- evidence of CSF flow obstruction

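### In Cohorts 2-5, unless the first two subjects are both C4, the second may be dosed 0 to 2 days after the first subject's Day 7 exam and MRI, and no rule requires these to be done or read

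*Protocol*

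**What the plan says.** Protocol 3.1.1 sets the spacing within Cohorts 2-5 by elapsed time: "with at least 8 days between administration of AST-OPC1 to the first and second subjects". A 14-day interval applies to consecutive subjects who both have a C4 neurological level, and it "would supersede the 8-day stagger noted above if the first two subjects in any cohort both have a C4 NLI". Once the first two subjects have been dosed without an SAE that would trigger suspension, the rest of the cohort may be dosed with no further stagger, apart from the C4 rule. SAP 3.2 repeats these rules.

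Section 3.1.2 gives the rationale. Nearly all surgical complications should show clinically within a few days, and SAEs are reported within 24 hours. It then continues: "In addition, subjects in this study will receive a complete neurological exam and MRI scan for safety monitoring at 7 days after AST-OPC1 injection".

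For Days 1-6, Section 7.4 schedules "Brief physical exam on Day 1", daily vital signs and chemistry, hematology on Day 1, a tacrolimus level around Day 3, concomitant medications and adverse events. The neurological exam, ISNCSCI exam and MRI first appear after injection in Section 7.5, at Day 7 with a window of one day either side. On imaging, Appendix E states: "All study-driven MRI reading will be performed by a central group of neuroradiologists". Images are sent to that group electronically, and neither document gives a read time.

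**The concern.** The rationale cites the Day 7 exam and MRI in support of the stagger, but the stagger itself does not mention them. A site can comply fully and still dose the second subject on the day of the first subject's first scheduled neurological exam, or before the Day 7 MRI has been read.

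The matter at stake is a finding, such as direct cord damage from the injection, that appears first on that exam or scan. It could then come to light after the next subject has been injected. The first pair matters most, because once two subjects have been dosed the remaining ones need no stagger unless they are consecutive C4 subjects.

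**Working it through.** **Inputs**

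- Minimum interval, first to second subject, Cohorts 2-5: 8 days (Protocol 3.1.1).
- Interval when both are C4: 14 days (3.1.1). Cohort 1 interval: 10 days (3.1.1).
- Day 7 visit window: Day 6, 7 or 8 (7.5 and Table 7-1).
- Day count: days after injection are positive (Protocol 7), and injection is Day 0 (SAP 4.4.1).
- MRI read time: not in the documents. Assumed range: 0 to 3 days.

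The documents state no figure for the gap, so there is none to reproduce.

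**Step 1. Days between the visit and the earliest next dosing**

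Gap = minimum interval − visit day.

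| Rule | Visit Day 6 | Visit Day 7 | Visit Day 8 |
|---|---|---|---|
| 8 days (Cohorts 2-5) | 8 − 6 = 2 | 8 − 7 = 1 | 8 − 8 = 0 |
| Same, read as dosing on Day 9 | 3 | 2 | 1 |
| 10 days (Cohort 1) | 4 | 3 | 2 |
| 14 days (both C4) | 8 | 7 | 6 |

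**Step 2. Does any other rule close the gap?**

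- The condition in 3.1.1 about suspension-triggering SAEs releases the remaining subjects after the first two. It does not govern the second.
- Under Section 5, sites notify the Sponsor at screening, "in order to ensure that the protocol specified rules for staggering within cohorts and for advancement to Cohorts 2-5 are followed correctly". This check enforces the stagger as written, which does not refer to the visit or the read.
- Under 7.14.2, if suspension occurs, "both enrollment of new subjects and administration of AST-OPC1 will be suspended". That acts on a finding once it is known. It does not require the exam to be done or the scan read first.
- Appendix E says who reads the scans, but ties no dosing decision to the read.

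I found no rule that makes the second dosing wait.

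**Step 3. Delay that a gate would add**

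Added delay = max(0, visit day + read days − 8).

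| Read time (assumed) | Visit Day 6 | Visit Day 7 | Visit Day 8 |
|---|---|---|---|
| 0 days | 0 | 0 | 0 |
| 1 day | 0 | 0 | 1 |
| 2 days | 0 | 1 | 2 |
| 3 days | 1 | 2 | 3 |

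The dosing window closes at Day 42 post-injury. With a 3-day delay, a candidate whose earliest permitted date under the 8-day rule falls on Day 40, 41 or 42 would pass it (42 − 3 = 39).

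**Step 4. Decisions still open at Amendment 3**

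The Amendment 3 rationale reports 17 subjects dosed. SAP 3.2.1 gives final cohort sizes of 3, 6, 6, 6 and 4, 25 in all. Taking Cohort 1 as complete, 17 − 3 = 14 subjects are spread over Cohorts 2-5, with at most 6, 6, 6 and 4. The advancement rules in 3.1.2 require:

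- Cohort 3 above 0 only if Cohort 2 has at least 5;
- Cohort 4 above 0 only if Cohort 2 has at least 2;
- Cohort 5 above 0 only if Cohort 3 has at least 2 and Cohort 4 at least 5.

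The feasible splits are:

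- Cohort 5 with 0 dosed: 9 (five with Cohort 2 at 6, four with Cohort 2 at 5).
- Cohort 5 with 1 dosed: 3.
- Cohort 5 with 2 dosed: 1.

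The total is 9 + 3 + 1 = 13. The smallest counts in any split are 5 for Cohort 2, 2 for Cohort 3 and 2 for Cohort 4, so the first pair in each of those cohorts had already been dosed. Only the Cohort 5 pair could still be open: it was in 12 of the 13 splits and was not in 1. Counting the opening of Cohort 5 as a further decision gives 0 to 2, but the advancement rules govern the opening, not the stagger. These are counts of possible splits, not probabilities.

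**The case against.** The strongest reply is that the plan has a coherent rationale that does not need the Day 7 visit. Serious surgical complications are expected within days, there is daily contact, adverse events are collected throughout Days 1-6, and SAEs reach the Sponsor within 24 hours. The exam and MRI are offered as additional support, so making them a gate goes beyond what the rule claims to do. This largely stands, and it keeps the point small. It does not answer the case of a finding first visible on the exam or scan: Section 3.1.2 speaks of nearly all complications, and itself brings in the Day 7 assessments.

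A second reply looks at what is new in each cohort. Cohort 2 raises only the concentration. Cohorts 4 and 5 repeat the doses of Cohorts 2 and 3. Only Cohort 3 introduces two injections and 100 µL, and it opens after a DMC review. That also stands. The pair that mattered most was Cohort 3's, already dosed by Amendment 3 in every feasible split. Cohort 5 was first at its dose only in AIS-B subjects.

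Third, the read time may be set in the imaging contractor's own documents and may be short. That is possible, but no dosing rule in the protocol depends on it.

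A reader might infer more than the documents support:

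- *That subjects go unwatched in Days 1-6.* Section 7.4 shows otherwise. What is missing before Day 7 is a scheduled formal neurological exam and MRI.
- *That a second subject was in fact dosed with the first subject's scan unread.* The documents give neither individual dosing dates nor read dates.
- *That the openings of Cohorts 4 and 5 share the flaw because 30 days of follow-up is not tied to the Day 30 visit.* That is an undefined term, and showing harm from it needs an assumed same-day enrollment. It is missing detail and is not pressed here.

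**Conclusion.** The point holds as a cheap improvement. Outside pairs who are both C4, the rule as written allows the second subject in Cohorts 2-5 to be dosed 2, 1 or 0 days after the first subject's first scheduled post-injection neurological exam, ISNCSCI exam and MRI, and nothing requires these to be completed or read. The 0-2 day figure is exact under the documents' day count. It becomes 1-3 if the interval is read as eight full intervening days.

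The practical weight for this trial is low. At most one affected pair remained at Amendment 3, and none if both Cohort 5 subjects were C4. Enrollment ended on 15 December 2017. The count of open decisions assumes that the current advancement rules and final cohort sizes applied to the first 17 subjects. The delay figures rest on the assumed 0-3 day read time. No endpoint or analysis is affected.

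**What to change.** Add to Protocol 3.1.1, for Cohorts 2-5: *the second subject may be dosed no sooner than 8 days after the first, and only once the first subject's Day 7 neurological exam is complete and the Day 7 MRI has had at least a documented preliminary read, with no finding that meets a suspension rule.* The 14-day C4 rule stays as it is. With enrollment closed, this applies to any further dosing under this protocol or a successor.

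The change is one sentence and uses assessments already scheduled. The price is a possible wait of 0-3 days for the second subject under the assumed read times, and the risk that a candidate near Day 42 post-injury misses the window. Scheduling the visit on Day 6 absorbs a read of up to 2 days, and accepting a preliminary read keeps the wait short.
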